APPENDIX VI: CORRELATIVE STUDIES GUIDE

Correlative Study	Appendix	Blood Volume			Tube Type
		Volume per sample	Total Volume ≥ 20 kg	Total Volume <20 kg	
Pharmacokinetics	VII; X	2-3 ml	30-45 ml	16-24 ml	K ₂ EDTA (lavender-top)
Pharmacodynamics	VIII	1 ml	5 ml	5 ml	Heparinized (green-top); Smart Tubes
Total Blood Volume		35-50 ml	21-29 ml		

THIS PROTOCOL IS FOR RESEARCH PURPOSES ONLY, SEE PAGE 1 FOR USAGE POLICY

APPENDIX VII: PHARMACOKINETIC STUDY FORM

COG Pt ID # _____ ACC # _____ **Day 1 of Protocol Therapy (XRT Start Date):** _____
 Please do not write patient names on this form or on samples.

Body Surface Area: _____ m² Dose Level: _____ mg/m² Patient weight: _____ kg
 Total Daily Dose: _____ mg

**Refer to [Appendix V-B](#) for PK collection based on XRT start date. **

Blood samples (2-3 mL) will be collected in K₂ EDTA (lavender-top) tubes in patients \geq 20 kg at the following time points (+/- 10 minutes): Baseline, PK Day 1 (pre-dose, 1 hr, 2 hr, 4 hr, 6 hr, 8 hr and 24 hours after dose), PK Day 5 (pre-dose, 1 hr, 2 hr, 4 hr, 6 hr, and 8 hr after dose), and PK Day 8 (pre-dose).

For patients $<$ 20 kg, samples will be collected at the following time points (+/- 10 minutes): Baseline, PK Day 5 (pre-dose, 1 hr, 2 hr, 4 hr, 6 hr, and 8 hr after dose), and PK Day 8 (pre-dose).

Blood Sample No.	Time Point**	Scheduled Collection Time**	Actual Date Sample Collected	Actual Time Sample Collected (24-hr clock)
0 ^{\$}	Baseline/Pre-study	Within 7 days prior to XRT start date	____ / ____ / ____	____ : ____
1 ^{\$, ^}	Baseline/PK Day 1	Prior to Monday dose	____ / ____ / ____	____ : ____
AZD1775 (MK-1775) Dose on PK Day 1**		Date: ____ / ____ / ____	Time: ____ : ____	
2 [^]	PK Day 1	1 hr after Monday dose	____ / ____ / ____	____ : ____
3 [^]	PK Day 1	2 hr after Monday dose	____ / ____ / ____	____ : ____
4 [^]	PK Day 1	4 hr after Monday dose	____ / ____ / ____	____ : ____
5 [^]	PK Day 1	6 hr after Monday dose	____ / ____ / ____	____ : ____
6 [^]	PK Day 1	8 hr after Monday dose	____ / ____ / ____	____ : ____
7 [^]	PK Day 2	24 (\pm 2) hrs after Monday dose [@]	____ / ____ / ____	____ : ____
8	PK Day 4	Prior to Thursday dose	No Longer Collected per AMD#3	
9	PK Day 5	Prior to Friday dose	____ / ____ / ____	____ : ____
AZD1775 (MK-1775) Dose on PK Day 5**		Date: ____ / ____ / ____	Time: ____ : ____	
Hematocrit Value on PK Day 5 (if available): _____				
10%	PK Day 5	1 hr after Friday dose	____ / ____ / ____	____ : ____
11	PK Day 5	2 hr after Friday dose	____ / ____ / ____	____ : ____
12	PK Day 5	4 hr after Friday dose	____ / ____ / ____	____ : ____
13	PK Day 5	6 hr after Friday dose	____ / ____ / ____	____ : ____
14	PK Day 5	8 hr after Friday dose	____ / ____ / ____	____ : ____
15	PK Day 8	Prior to Monday dose	____ / ____ / ____	____ : ____
AZD1775 (MK-1775) Dose on PK Day 8**		Date: ____ / ____ / ____	Time: ____ : ____	

^{\$}Baseline samples should be taken at least 1 day apart, if feasible.

[^] Patients \geq 20 kg only

**Refer to [Appendix V-B](#) for PK collection based on XRT start date.

[@] Hold Dose until PK sample is collected.

One copy of this Pharmacokinetic Study Form should be uploaded into RAVE. A second copy should be sent with the samples to the address listed in [Section 8.4.6](#). See [Section 8.4](#) and [Appendix XI](#) for detailed guidelines for packaging and shipping PK samples.

Signature: _____
 (site personnel who collected samples)

Date: _____

THIS PROTOCOL IS FOR RESEARCH PURPOSES ONLY, SEE PAGE 1 FOR USAGE POLICY

APPENDIX VIII: PHARMACODYNAMIC STUDY FORM

COG Pt ID # _____ ACC # _____ **Day 1 of Protocol Therapy (XRT Start Date):** _____
Please do not write patient names on this form or on samples.

Body Surface Area: _____ m² Dose Level: _____ mg/m² Total Daily Dose: _____ mg

Blood samples will be obtained from all patients (1 ml per time point) prior to treatment start (two baseline samples are required) as well as at the following time points. Every effort should be made to obtain the baseline (pre-treatment) samples on two different days, if feasible. A total of 5 time points for the PD analysis will be collected.

Blood Sample No.	Time Point**	Scheduled Collection Time**	Actual Date Sample Collected	Actual Time Sample Collected (24-hr clock)
1*	Baseline/Pre-study	Within 7 days prior to XRT start date	/ /	_____ :____
2*	Baseline/ PD Day 1	Prior to Monday dose	/ /	_____ :____
AZD1775 (MK-1775) Dose on PD Day 1**		Date: ____ / ____ / ____	Time: ____ ____ : ____ ____	
3	PD Day 1	6-8 hr after Monday dose	/ /	_____ :____
AZD1775 (MK-1775) Dose on PD Day 5**		Date: ____ / ____ / ____	Time: ____ ____ : ____ ____	
4	PD Day 5	6-8 hr after Friday dose	/ /	_____ :____
5	PD Day 8	Prior to Monday dose	/ /	_____ :____
AZD1775 (MK-1775) Dose on PD Day 8**		Date: ____ / ____ / ____	Time: ____ ____ : ____ ____	

*Baseline samples should be taken at least 1 day apart, if feasible.

**Refer to [Appendix V-B](#) for PD collection based on XRT start date.

One copy of this Pharmacodynamic Study Form should be uploaded into RAVE. A second copy should be sent with the samples to the address listed in [Section 8.5.5](#). See [Section 8.5](#) for detailed guidelines for packaging and shipping PD samples.

Record any notes for Sample Storage Conditions below.

Notes:

If this form will be used as a source document, the site personnel who collected the samples must sign and date this form below:

Signature: _____
(site personnel who collected samples)

Date: _____

APPENDIX IX: PD SAMPLE COLLECTION GUIDELINES**Required Items:**

- Whole blood collection at required PD time points as outlined in [Appendix VIII](#)
- Smart Tubes at room temperature (one per incubation condition): will be provided by study team
- Water bath pre-warmed to 37°C
- -80°C freezer or dried ice
- Complete RPMI (optional)

Protocol:

1. Use an approved tube containing sodium heparin (i.e. green top Vacutainer) to collect PD sample. Ensure good mixing with the anticoagulant by inverting the securely capped tube at least 6 times. Begin incubation of the blood with the Smart Tube system as soon as possible, ideally within two hours of the blood draw. Keep the blood at room temperature until it is assayed with the Smart Tube system.
2. Add 1 milliliter (ml) of the whole blood sample to each Smart Tube. Immediately cap the Smart Tube and vortex or invert six times to ensure good mixing with the agents added.
3. Place the Smart Tubes in the 37°C water bath for 30 minutes.
4. At the end of the 30 minutes incubation time remove the Smart Tubes from the water bath and activate the Smart Tubes manually. To activate a Smart Tube manually, make sure the cap is screwed on securely and then bend the Smart Tube in the middle until you feel the ampoule inside break, then invert the Smart Tube 10 times to ensure good mixing (gently shaking the Smart Tube up and down 10 times is an acceptable alternative to inverting it 10 times).
5. Incubate the activated Smart Tubes at room temperature for 8 minutes.
6. Immediately transfer the Smart Tubes to a -80°C freezer or place in direct contact with dry ice. The Smart Tubes should be stored at -80°C until the sample is analyzed. Samples frozen in Smart Tubes should not be stored at temperatures warmer than -80°C. Smart Tubes have not been validated for storage in liquid nitrogen. Samples will be stored at -80°C and shipped when all PD time points have been collected. Tubes need to be shipped on dry ice. All samples should be shipped to address as outlined in [Section 8.5.5](#). Samples should NOT be shipped on a Friday or before a holiday.

THIS PROTOCOL IS FOR RESEARCH PURPOSES ONLY, SEE PAGE 1 FOR USAGE POLICY

APPENDIX X: TOXICITY SPECIFIC GRADING**Bilirubin**

Grade 1:	> ULN - \leq 1.5 x ULN
Grade 2:	> 1.5 x ULN - 3.0 x ULN
Grade 3:	> 3.0 x ULN -10.0 x ULN
Grade 4:	> 10.0 x ULN

ALT: For the purpose of this study, the ULN for SGPT is 45 U/L regardless of baseline.

Grade 1:	> 45 U/L - \leq 135 U/L
Grade 2:	136 U/L -225 U/L
Grade 3:	226 U/L - 900 U/L
Grade 4:	> 900 U/L

AST: For the purpose of this study, the ULN for SGOT is 50 U/L regardless of baseline.

Grade 1:	> 50 U/L - \leq 150 U/L
Grade 2:	151 U/L -250 U/L
Grade 3:	251 U/L -1000 U/L
Grade 4:	> 1000 U/L

GGT:

Grade 1:	> ULN- 2.5 x ULN
Grade 2:	> 2.5 x ULN - 5.0 x ULN
Grade 3:	> 5.0 x ULN -20.0 x ULN
Grade 4:	> 20.0 x ULN

APPENDIX XI: PREPARATION OF PLASMA SAMPLES FOR AZD1775 (MK-1775) PK ASSESSMENT

I. Biosafety

It is essential that universal precautions be taken while working with these specimens. However, you are encouraged to wear gloves and a lab coat/gown at all times to ensure safe handling of samples. If you should tear a glove, remove the torn one and replace it immediately.

II. General Instructions

Collect venous blood in a purple-topped vacutainer containing K₂EDTA.

III. Sample Preparation:

Material Needed:

1. Purple-topped vacutainer evacuated blood collection tubes (containing K₂EDTA)
2. 3.6 mL NUNC internal thread round bottom cryotubes (NUNC Part #366524) for plasma

Collection of Blood

For specific time points of sample collection, please refer to [Appendix VII](#) and [Appendix V-B](#).

Procedure

1. Samples in the blood collection tube will be centrifuged at between 1000-1300 RCF (x g) at between 4°C to 10°C for 10 minutes. If the samples cannot be centrifuged immediately, the tubes should be kept on ice and centrifuged within 30 minutes of collection.

Note: RCF varies according to the centrifuge rotor radius. The formula for computing RCF from rotation speed and centrifuge radius is RCF = 11.2r (RPM/1000)², where r is rotor radius, in cm, and RPM is the rotations per minute setting of the centrifuge.

2. Immediately after separation of the whole blood, carefully transfer the plasma (**about 0.5 - 1.0 mL**) using a plastic pipette into a labeled 3.6 mL internally-threaded NUNC cryotube and store at -20°C until shipment on DRY ICE.

Note: In the event that the whole blood samples cannot be processed immediately the samples should be kept on ice. No more than 60 minutes should elapse between blood draw and the freezing of plasma samples.

IV. Laboratory Contact and Shipping Instructions

It is the responsibility of the primary investigator to ensure that all staff personnel who will be handling, packaging, and/or shipping clinical specimens act in conformance with International Air Transport Association (IATA) regulations relating to the handling and shipping of hazardous goods.

1. AZD1775 (MK-1775) plasma shipments will be made in freezer boxes containing at least 10 kg DRY ICE.
2. Please include the PK Study Form ([Appendix VII](#)) with each shipment.
3. Shipments should be sent via overnight Federal Express, Monday through Wednesday to assure receipt by Friday. All samples should be shipped to the address in [Section 8.4.6](#).

THIS PROTOCOL IS FOR RESEARCH PURPOSES ONLY, SEE PAGE 1 FOR USAGE POLICY

APPENDIX XII: POTENTIAL DRUG INTERACTIONS WITH AZD1775 (MK-1775)

The lists below do not include everything that may interact with chemotherapy. Study Subjects and/or their Parents should be encouraged to talk to their doctors before starting any new medications, using over-the-counter medicines, or herbal supplements and before making a significant change in diet.

AZD1775 (MK-1775)

Drugs that may interact with AZD1775 (relevant drugs listed by generic name)

• Some antibiotics (chloramphenicol, ciprofloxacin, clarithromycin, erythromycin, norfloxacin, rifabutin, rifampin, telithromycin)• Some antidepressants (fluoxetine, fluvoxamine, nefazodone)• Some antiepileptics (carbamazepine, oxcarbazepine, phenobarbital, phenytoin)• Some antifungals (fluconazole, itraconazole, ketoconazole, posaconazole, voriconazole)• Some antiretrovirals and antivirals (boceprevir, delavirdine, efavirenz, indinavir, nelfinavir, nevirapine, ritonavir, saquinavir)• Some heartburn medications (cimetidine, omeprazole, lansoprazole, rabeprazole)• Some cholesterol lowering medications (atorvastatin, pravastatin, rosuvastatin, simvastatin)• Several other specific agents, including the following:
○ Aprepitant/fosaprepitant○ Amiodarone○ Barbiturates○ Diazepam○ Diltiazem○ Imatinib○ Metformin○ Mifepristone○ Modafinil○ Pioglitazone○ Verapamil

Food and supplements* that may interact with AZD1775

• Echinacea• St. John's Wort• Some fruits and juices: grapefruit, grapefruit juice, Star fruit

**Supplements may come in many forms such as teas, drinks, juices, liquids, drops, capsules, pills, and dried herbs. All forms should be avoided.*

APPENDIX XIV: INSTRUCTIONS FOR TREATING DIARRHEA

Institutional practice may be used in place of these guidelines.

At the first episode of poorly formed or loose stools or the earliest onset of bowel movements more frequent than normally expected for the patient, initiate infectious evaluation including but not limited to bacterial culture, *c. difficile* toxin, viral infection (i.e. adenovirus, norovirus, rotavirus, enterovirus, CMV). If studies are negative, initiate loperamide (dosing below).

Any patient with diarrhea who is not already admitted to the hospital should be admitted for close monitoring for the occurrence of blood or black stools, symptoms of dehydration, fever, inability to take liquids by mouth, and inability to control diarrhea within 24 hours of using loperamide or other prescribed antidiarrheal medications.

Patients will be given **loperamide** based on body weight. Loperamide may be discontinued when diarrhea has resolved for 12 hours.

LOPERAMIDE DOSING RECOMMENDATIONS	
(NOTE: maximum dose of loperamide for adults is 16 mg/day)	
ALL patients: discontinue loperamide when the patient is no longer experiencing significant diarrhea.	
Weight (kg)	ACTION
<13 kg	Take 0.5 mg (2.5 mL [one-half teaspoonful] of the 1 mg/5 mL oral solution) after the first loose bowel movement, followed by 0.5 mg (2.5 mL [one-half teaspoonful] of the 1 mg/5 mL oral solution) every 3 hours. During the night, the patient may take 0.5 mg (2.5 mL [one-half teaspoonful] of the 1 mg/5 mL oral solution) every 4 hours. Do not exceed 4 mg (20 mL or 4 teaspoons) per day.
≥ 13 kg to < 20 kg	Take 1 mg (5 mL [1 teaspoonful] of the 1 mg/5 mL oral solution or one-half capsule or tablet) after the first loose bowel movement, followed by 1 mg (5 mL [one teaspoonful] of the 1 mg/5 mL oral solution) every 3 hours. During the night, the patient may take 1 mg (5 mL [one teaspoonful] of the 1 mg/5 mL oral solution) every 4 hours. Do not exceed 6 mg (30 mL or 6 teaspoons) per day.
≥ 20 kg to < 30 kg	Take 2 mg (10 mL [2 teaspoons] of the 1 mg/5 mL oral solution or 1 capsule or tablet) after the first loose bowel movement, followed by 1 mg (5 mL [one teaspoonful] of the 1 mg/5 mL oral solution or one-half capsule or tablet) every 3 hours. During the night, the patient may take 2 mg (10 mL [2 teaspoons] of the 1 mg/5 mL oral solution or 1 capsule or tablet) every 4 hours. Do not exceed 8 mg (40 mL or 8 teaspoons) per day.

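### In two rows of the Appendix XIV loperamide table, a full day at the printed intervals, night doses included, adds up to more than the daily maximum in the same row

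*Combined protocol and SAP*

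**What the plan says.** The loperamide table in Appendix XIV has the same four parts in each row.

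- **< 13 kg.** A dose of 0.5 mg "after the first loose bowel movement, followed by 0.5 mg (2.5 mL [one-half teaspoonful] of the 1 mg/5 mL oral solution) every 3 hours"; then "During the night, the patient may take 0.5 mg (2.5 mL [one-half teaspoonful] of the 1 mg/5 mL oral solution) every 4 hours"; ceiling "Do not exceed 4 mg (20 mL or 4 teaspoons) per day".
- **13 to < 20 kg.** The opening dose is 1 mg. The daytime instruction is "followed by 1 mg (5 mL [one teaspoonful] of the 1 mg/5 mL oral solution) every 3 hours"; for the night the row adds "During the night, the patient may take 1 mg (5 mL [one teaspoonful] of the 1 mg/5 mL oral solution) every 4 hours"; ceiling "Do not exceed 6 mg (30 mL or 6 teaspoons) per day".
- **20 to < 30 kg.** First dose 2 mg, then 1 mg at 3-hour intervals, with 2 mg at 4-hour intervals permitted at night; ceiling "Do not exceed 8 mg (40 mL or 8 teaspoons) per day".

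The appendix also lets a site use its own practice instead, and allows loperamide to stop once diarrhea has been absent for 12 hours. It does not say how long a night is. No row says which doses fall away when the ceiling is reached.

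**The concern.** A row that gives both a schedule and a ceiling should let the reader give the schedule for a day and stay within the ceiling, or say how the ceiling cuts the schedule short. The < 13 kg row does the first. The next two rows do neither: each permits night doses that, after daytime dosing at the printed interval, carry the total past the limit printed a sentence later.

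What is at stake is the clarity of a safety instruction for small children. Section 2.1 lists gastrointestinal toxicity among the expected effects of AZD1775, so the table is likely to be needed. Two people dosing from the same row could give different totals, depending on whether they look first at the intervals or at the limit.

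**Working it through.** **Inputs from Appendix XIV** (first dose / 3-hourly dose / night dose / ceiling, in mg): < 13 kg 0.5 / 0.5 / 0.5 / 4; 13 to < 20 kg 1 / 1 / 1 / 6; 20 to < 30 kg 2 / 1 / 2 / 8.

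**Assumptions, not in the document.** The day is the 24 hours from the first dose. Daytime doses fall every 3 hours while awake. Night doses follow every 4 hours after the last daytime dose, and all of them are taken. The night lasts 8 hours in the base case, with a range of 6 to 12. On later days the first dose of the day is the ordinary 3-hourly dose; this matters only for 20 to < 30 kg.

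**Formula.** Total = first dose + (daytime doses − 1) × 3-hourly dose + night doses × night dose.

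**Dose times**
- Night of 6 or 8 h: day at hours 0, 3, 6, 9, 12, 15 (6 doses); night at 19, 23 (2 doses).
- Night of 9 or 10 h: day at 0, 3, 6, 9, 12 (5); night at 16, 20 (2).
- Night of 12 h: day at 0, 3, 6, 9 (4); night at 13, 17, 21 (3).

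**The ceiling that is reproduced.** For < 13 kg with an 8 h night: 0.5 + 5 × 0.5 + 2 × 0.5 = 4.0 mg, exactly the printed 4 mg.

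**The two that are not, first day, 8 h night**
- 13 to < 20 kg: 1 + 5 × 1 + 2 × 1 = 8 mg against 6.
- 20 to < 30 kg: 2 + 5 × 1 + 2 × 2 = 11 mg against 8.

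Both pass the ceiling at hour 19, the first night dose.

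**Range over night length (mg)**

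| Row | Ceiling | Night 6–8 h | Night 9–10 h | Night 12 h |
|---|---|---|---|---|
| < 13 kg | 4 | 4.0 | 3.5 | 3.5 |
| 13 to < 20 kg | 6 | 8 | 7 | 7 |
| 20 to < 30 kg, first day | 8 | 11 | 10 | 11 |
| 20 to < 30 kg, later day | 8 | 10 | 9 | 10 |

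The excess is 7/6 − 1 = 17% to 8/6 − 1 = 33% in the middle row, and 9/8 − 1 = 12.5% to 11/8 − 1 = 37.5% in the heaviest.

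**When the ceilings do hold**
- No night doses, 16 h day, first day: 6 × 1 = 6 mg and 2 + 5 × 1 = 7 mg, both within limits.
- 13 to < 20 kg at 4-hourly intervals throughout: 6 × 1 = 6 mg, all of the ceiling. A single 3-hour gap (hours 0, 3, 7, 11, 15, 19, 23) makes it 7 mg.
- 20 to < 30 kg on a later day, 1 mg every 3 hours round the clock and no 2 mg night doses: 8 × 1 = 8 mg.

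**Room left for night doses after the daytime doses**
- 8 h night: 6 − 6 = 0 mg in the middle row, so none fits. In the heaviest row 8 − 7 = 1 mg on the first day, against a night dose of 2 mg, so none fits; on later days 8 − 6 = 2 mg, so one of the two fits.
- 10 h night, first day: 6 − 5 = 1 mg and 8 − 6 = 2 mg, so one of the two fits in each row.

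**The case against.** The strongest reply is that the ceiling is part of the row and governs it. A child dosed by the whole row stops at 6 or 8 mg. A reader might infer that following the table as written takes a child over the limit, or that schedule and limit can never both be respected. The documents support neither: an interval with a cap can be followed until the cap is reached, the night doses are optional, and a 16-hour day without them stays inside both limits. Nor is a full 24 hours of dosing the default, since loperamide may stop on resolution and institutional practice may replace the table.

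All of that stands, and it limits the weight of the point. It does not remove the defect. Both rows expressly permit night doses that cannot all be given within their own ceiling after daytime dosing at the printed interval, and the reader must guess which to drop.

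Three further inferences should be resisted.
- **Effect on DLTs.** Section 5.5 has no duration exemption for diarrhea, but a DLT needs attribution to AZD1775, and nothing in the documents shows that stopping loperamide at the ceiling changes the grade reached.
- **Number of children affected.** The documents give no weight distribution.
- **The night rate for 20 to < 30 kg.** It is higher than the day rate (2/4 = 0.50 against 1/3 = 0.33 mg per hour), the reverse of the other rows. That is unusual, but no rule in the appendix forbids it.

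**Conclusion.** The concern holds in a limited form. For a full 24 hours with the night doses taken, the printed intervals give 7 to 8 mg against 6 mg (13 to < 20 kg) and 9 to 11 mg against 8 mg (20 to < 30 kg). The direction does not change over nights of 6 to 12 hours, or between first and later days; the size does. How many night doses fit under the ceiling also depends on the assumed night. The < 13 kg row is consistent.

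This is an internal inconsistency in optional supportive-care guidance that carries an explicit cap. It is a minor patient-safety correction, with no bearing on endpoints, dose-escalation or DLT rules, sample size or analysis. The arithmetic does not show whether an interval dose or a maximum is the figure at fault. The count covers the three weight bands below 30 kg only.

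**What to change.** Reconcile the first, 3-hourly and night doses with the daily maximum in the 13 to < 20 kg and 20 to < 30 kg rows of Appendix XIV, so that the row no longer offers doses its own limit rules out. Apply the same 24-hour count to any heavier weight bands. Which figure changes is for the clinical team and pharmacist; this review takes no position on it. The cost is a correction to one appendix table at the next amendment, with no effect on enrolment, data collection or analysis.
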